Randomized controlled trial of awake transnasal laser-assisted surgery (TNLS) and microlaryngeal surgery for vocal cord cyst

CREC Ref No: 2023.644-T

Background

Office-based awake transnasal laser-assisted surgery (TNLS) has been gaining popularity in treating different laryngeal lesions, with the advantages of avoiding general anesthetic risks and minimizing healthcare-related costs. ⁽¹⁻⁴⁾ In addition, the general waiting time for surgeries under general anesthesia in public hospitals is getting longer due to the increasing population and limited resources. We have recently conducted a novel randomized controlled trial in 2021-2022 comparing the functional and cost-effectiveness of traditional microlaryngeal surgery (MLS) under general anesthesia and TNLS for benign laryngeal lesions (vocal cord polyps, nodules, cysts, granuloma and Reinke's edema), and found that TNLS was superior to MLS in terms of length of stay, intraoperative complications, perioperative throat discomfort and hospital costs; while it was equivalent to MLS in terms of functional outcome, operative time and recurrence rate. ⁽⁵⁾ However, since our previous study's main goal was to compare TNLS to MLS in a macroscopic perspective in terms of functional outcomes and cost-effectiveness, it had included a wide variety of benign laryngeal lesions, and different vocal cord lesions may respond differently to laser surgery.

Vocal cord cyst is a fluid-filled sac inside the vocal cord, with 2 subtypes: 1) Epidermoid cyst due to epithelial inclusion 2) Mucous retention cyst due to glandular ductal obstruction. Vocal cord cysts typically do not resolve with voice therapy, and are traditionally excised with microlaryngeal surgery with microflap technique or marsupialization. ^(6,7) In our previous RCT study, subgroup analysis did not show a significant difference of vocal cord cyst recurrence in both TNLS and MLS group. However, our cohort had a higher overall vocal cord cyst recurrence rate (13.8%) compared to historic cohort rate of 2.2-8.7%^(5, 8), which may be accounted by that our vocal cord cysts were ablated and marsupialized instead of removed in the TNLS group. Nevertheless, a recent case series by Gao and colleagues showed a good functional outcome of awake KTP-laser marsupialization in selected cases. ⁹ A larger cohort is warranted to compare TNLS to MLS for vocal cord cyst. Therefore, our authors would like to conduct a randomized controlled trial to compare tradition MLS surgery to TNLS, with hypothesis that TNLS would be non-inferior to traditional microlaryngeal surgery in benign laryngeal lesions, and with its additional benefits on minimization of anesthetic risks and hospital expenses, hopefully to expand its further application.

Methodology

Study setting

This is a prospective, single-cluster randomized controlled trial conducted at two tertiary referral hospitals (Prince of Wales Hospital and Alice Ho Miu Ling Nethersole Hospital, NTEC) in Hong Kong to compare the clinical and functional outcomes of office-based TNLS to traditional microlaryngeal surgery under general anesthesia for vocal cord cysts.

Eligibility criteria

All consecutive patients with vocal cord cysts interested in operative management will be screened for eligibility.

Inclusion criteria

Patients who are (i) older than 18-year-old; (ii) able to independently provide consent; and (iii) able to tolerate flexible laryngoscopy would be recruited.

Exclusion criteria

Patients who are (i) under 18-year-old; (ii) unable to independently give an informed consent; (iii) unable to tolerate flexible laryngoscopy; (iv) allergic to local anesthesia; (v) had unfavorable anatomy such as prolapsing epiglottis precluding adequate visualization, extensive lesions and an expected difficult operation as judged by the surgeons; and (vi) with pathologies other than vocal cord cyst would be excluded from the study.

Study intervention

The active comparator is traditional microlaryngeal surgery under general anesthesia, which is the standard surgical care for vocal cord cyst at our institution. The experimental intervention would be awake transnasal laser-assisted surgery under local anesthesia, carried out in minor operation theater as a day-case basis in ENT ambulatory center.

Microlaryngeal surgery (MLS)

For traditional MLS under general anesthesia, the patient is admitted on the same day morning of the surgery with prior outpatient anesthetist assessment, or one day earlier to receive inpatient anesthesia assessment in special cases. The patient will be kept fast according to anesthetist assessment before surgery begins. After general anesthesia and intubation with microlaryngeal tube, the patient would be positioned on head-ring support for better alignment and access to glottis. After insertion of teeth guard, a laryngoscope will be inserted transorally under direct vision, and suspended with chest table support. Vocal cord cysts are visualized with microscope, and removed with microsurgery instruments with microflap technique and sent for routine section. Hemostasis is ascertained, then the laryngoscope is removed carefully under direct vision and injuries to pharyngeal walls, tongue base, teeth, lips and temporomandibular joints are checked. After the surgery, the patient is kept nil-by-mouth until fully awake, and is discharged on same day or the next day depending on the post-operative recovery. Patient will be discharged with voice rest for 3 days and prescription of Pantoprazole 40mg daily 4 weeks and Paracetamol as needed.

Awake transnasal laser-assisted surgery (TNLS)

For TNLS, patients are admitted to the day ward center on the same morning or afternoon of the surgery with fasting prior 6 hours. Physical examination would be repeated to ensure that the patient is fit and able to tolerate transnasal laser surgery under local anesthesia. The surgery would be done by or under supervision of ENT specialists with laryngeal laser experience. Following administration 2-4 puffs of 5% lidocaine/0.5% phenylephrine (Co-phenylcaine) nasal spray and 2 puffs of 10% oral Xylocaine spray, a transnasal channel flexible laryngoscope is introduced. The epiglottis, laryngeal inlet and subglottis are further anesthetized with 3ml 2% xylocaine during phonation via working channel. Adequacy of anesthesia is confirmed with absence of gag reflex or discomfort when gently palpating the epiglottis and arytenoids with endoscope tip. Should the patient still have insufficient anesthesia, another 1-2ml 2% xylocaine will be injected with 20G needle for superior laryngeal nerve block. The total dose of local anesthesia shall not exceed maximum dose per kg body weight. A 445nm blue laser is introduced via a working channel of bronchoscope and laser ablation of vocal cord cyst is performed. During the operation, patient will receive continuous SpO2 monitoring with regular blood pressure monitoring. Standardized emergency trolley will be available in case of airway emergency. After the procedure, patients are kept nil-by-mouth for 2 hours until anesthesia wears off, meanwhile with close observation in day ward with continuous SpO2 monitor for 1 hour. Patients will be discharged on the same day of the procedure, with voice rest for 3 days and prescription of Pantoprazole 40mg daily 4 weeks and Paracetamol as needed.

Laser safety

Laser surgery is regarded as a high-risk aerosol generating procedure during the COVID pandemic. Full personal protective equipment with N95 mask, laser eye-shield would be worn by all team members throughout the laser surgery. Doctors and nurses participating in the surgery would receive prior laser surgery safety training. For patients who are on anticoagulant or antithrombotics, the medications will be withheld according to our local hospital guideline balancing on the bleeding and thrombotic risks.

Recruitment and Pre-operative assessment, Consent and Withdrawal of consent

All eligible patients will be assessed in our out-patient clinic in a standardized manner as follow:

1. History taking
2. Complete head and neck physical examination
3. Flexible laryngoscopy for confirmation of diagnosis, with photo documentation of site and size (in relative to length of vocal cord in full abduction)

Diagnosis would be explained to patients, and management options of conservative, microlaryngeal surgery under general anesthesia, and TNLS with their pros and cons would be discussed. Patient information sheet and informed consent are provided to facilitate the

process. Should the patient decide to participate in the study, consent of the study would be signed in the same clinic session. Patient would be informed of his randomized treatment group, and consent of the surgery would be also signed in the same section. Participation is voluntary and any study subject can decide to withdraw at any time of the study period. Upon study withdrawal, the patient will continue to receive standard treatment according to disease status.

In addition to above mentioned assessments, patient would also be assessed in a multidisciplinary voice clinic undergoing a detailed voice assessment co-organized with speech language pathologist, including Voice-Handicap Index (VHI-30), perceptual evaluation of voice, acoustic voice analysis, aerodynamic measures and laryngeal imaging.

Failure of study intervention

When patients cannot tolerate the allocated intervention, for example patients randomized to MLS group but contraindicated to general anesthesia, or patients randomized to TNLS but cannot tolerate transnasal laser surgery due to discomfort or anxiety, can crossover to other study arm. Outcomes would be analyzed by intention-to-treat principle.

Follow-up schedule

All patients would have follow-up in a multi-disciplinary voice clinic on post-op 2 weeks, 6 weeks, 3 months, 6 months and 1 year. During the postoperative follow-ups, patients are required to fill in a questionnaire and undergo voice assessments as mentioned above.

Primary outcome

The primary outcome was to compare the pre- and post-operative Voice-Handicap Index (VHI-30) of TNLS and MLS groups. The VHI-30 is a 30-item self-administered questionnaire, which has been shown to be a reliable measure for voice treatment outcome.^(10,11) It consists of three subscales, namely physical, functional and emotional. It provides an overall measurement of a person's vocal function and how it influences a person's everyday functioning and experience.

Secondary outcomes

The secondary outcomes included other voice-related outcomes (i.e. perceptual analysis, acoustic voice analysis, aerodynamic measure, visual analog scale (VAS) on voice quality), procedure-oriented outcomes, patient-oriented outcomes and hospital costs. Perceptual evaluation of voice using the GBRAS scale, in which patients would be required to produce sustained vowel and connected speech voice samples. Two experienced speech-language pathologists blinded to the patient's information would rate the audio recordings. For acoustic voice analysis, it would be conducted using PRATT program with parameters including

jitter, shimmer, noise-to-harmonic ratio measures and cepstral peak performance. For aerodynamic measure, maximal phonation time (MPT) would be measured by instructing patients to phonate /a:/ sound for as long as possible after maximal inspiration, at a spontaneous, comfortable pitch and loudness level, for three consequent trials. In VAS, patients would be asked to self-rate their voice quality on a visual analog scale of 0 (best) to 10 (worst). Videostroboscopy would be conducted on all patients to identify any anatomical and physiological changes, which included presence of laryngeal pathology, vocal fold closure pattern, and mucosal wave pattern.

Procedure-oriented outcomes include operation time, completeness of lesion removal, complications in Clavien-Dindo classification, length of hospital stay, disease recurrence rate, and reoperation.

Patient-oriented outcomes included peri-operative throat, nose, and overall discomfort in visual analogue scale, a 10-point scale with 0 (least uncomfortable) to 10 (most uncomfortable).

Medical costs of both interventions would be also calculated respectively, including costs for inpatient hospital stay, medical staff, operating theater and consumables.

Sample size calculation

Power calculation demonstrated that with a sample size of 21 per group, a two-arm study has a power of 80% to demonstrate a non-inferiority margin 7 absolute score, with one-sided significance of 0.05 regarding the primary outcome parameter, i.e. VHI-30. The calculation was based on published data from Misono et al.¹² in which a VHI-30 score over 16 was determined as a minimal important difference. Assuming a 20% drop-out rate, at least 54 patients were required, with 27 patients in each arm.

Participant timeline

TIMEPOINT	D1	Allocation	Post-allocation		Close-out
	Pre-op assessment	Intra-operative	Immediate post-operative	FU at 2w, 6w, 3mo, 6mo, 1y	
Enrolment					
Eligibility screen	X				
Informed consent	X				
Randomization					
MLS		X			
TNLS		X			
Assessment					
Demographics	X				
	X				
	X				
	X				
	X				
	X				
Disease					
Type of lesion	X				
Site of lesion	X				
Size of lesion	X				
FL / Videostroboscopy	X		X		X
Anaesthetic assessment					
ASA	X				
Functional assessment					
VHI30	X				X
Other secondary voice-related outcomes (MPT, Acoustic analysis etc)	X				X
Procedural data					
Operation time		X		X	
Peri-op tolerance scale		X		X	
Peri-op pain score		X		X	
Post-operative outcome					
LOS			X		
Residual lesion			X		X
Complications			X		X
Recurrence					X
Reoperation					X
Pathology					X

Randomization

Patients are randomized to receive either MLS under general anesthesia or TNLS under local anesthesia. Block randomization is used to ensure equal distribution between two treatment arms. To avoid selection bias, the blocking mechanism is designed by a third party not involved in the study, and is not disclosed to investigators. Randomization is only performed on the day of recruitment, which the recruiter shall contact the third party for the result randomized treatment group. Both the patients and the laryngologists cannot be blinded due to the nature of operation.

Statistical method

All outcome measurements will be analyzed with an intention-to-treat principle. Independent samples t-test will be used for parametric continuous variables; Mann-Whitney U test will be used for non-parametric continuous variables; chi-square test will be used for categorical variables. A p-value less than 0.05 will be considered to be statistically significant. All statistical analysis will be performed using SPSS version 26.0.

Data monitoring and confidentiality

Patient demographics and clinical data are obtained from a territory-wide electronic medical record system named as Clinical Management System (CMS). Individual patient medical information obtained as a result of this study is considered strictly confidential and disclosure to third parties is prohibited. Only the principal investigator, co-investigators, study personnel and research assistants assigned for data collection with the approval of the principal investigator are allowed to have access of the data. Full access to the final data set will be reserved for the principal investigator and the statistician involved in this study. All information will be stored in a password protected hospital authority computer and a locked file cabinet with the key kept by the principal investigator. An Prince of Wales Hospital ENT specialist not involved in the study and with surplus experience on laryngeal surgery will be responsible for safety monitoring. Names of participants will not be used. Information will be retained for a minimum of 10 years after study completion, after which all data will be completely destroyed without any identifiable personal information. All serious adverse events will be reported to the committee within 24 hours.

Research ethics approval and protocol amendments

Approval will be obtained from the Joint Chinese University of Hong Kong – New Territories East Cluster Clinical Research Ethics Committee, which is the institutional review board of our university. The study will be conducted in accordance with the Declaration of Helsinki and the International Conference on Harmonisation, Good Clinical Practice Guidelines (ICH-GCP). Prior approval from the committee and the designated trial registry will be obtained prior to implementation of important protocol modifications.

Access to data

The Chinese University of Hong Kong will control the final trial dataset. Any requests for data access can be made to the lead principal investigator. A detailed plan with specific objectives and types of data request has to be formulated and submitted. Upon approval, the requested information will be available, on request to the corresponding author.

Dissemination policy

The results of the study will be presented at relevant international conferences and published in peer-review journals.

Reference

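### Complications: an end-of-procedure injury search is named only for microlaryngeal surgery, and events are counted only by allocated arm, so minor events may be detected unequally and the complication profile of each procedure is blurred

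*Protocol*

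**What the plan says.** **Procedure descriptions.** The Protocol section on MLS describes a rigid instrument: "a laryngoscope will be inserted transorally under direct vision, and suspended with chest table support". When it is withdrawn, "injuries to pharyngeal walls, tongue base, teeth, lips and temporomandibular joints are checked". The section on TNLS describes a transnasal flexible scope and a laser: "A 445nm blue laser is introduced via a working channel of bronchoscope and laser ablation of vocal cord cyst is performed". It provides for oxygen saturation and blood pressure monitoring during the operation and, afterwards, "meanwhile with close observation in day ward with continuous SpO2 monitor for 1 hour". It names no inspection for injury at the end of the procedure.

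**Outcome and schedule.** Secondary outcomes lists "complications in Clavien-Dindo classification" among the procedure-oriented outcomes. The Participant timeline has one complications row for both arms. It is marked under the immediate post-operative column and again in the last column, with no apparent mark under the intra-operative column. The table layout is partly broken in the copy read. Laryngoscopy or videostroboscopy is marked in the same two post-operative columns.

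**Crossover and analysis.** Failure of study intervention permits crossover from either arm to the other. Statistical method says: "All outcome measurements will be analyzed with an intention-to-treat principle".

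**Prior claim.** Background reports that the group's earlier trial "found that TNLS was superior to MLS in terms of length of stay, intraoperative complications, perioperative throat discomfort and hospital costs".

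**The concern.** Two separate matters affect the same secondary outcome.

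*Ascertainment.* One arm has a named search for minor injury at the end of the operation. For the other, the protocol does not say what is looked for at that moment, although an instrument passes through the nose and a laser is fired at the vocal cord. Randomization states that patients and laryngologists cannot be blinded, and blinded raters are named only for the voice recordings. Clavien-Dindo grades an event once it has been found; it does not make finding it equally likely. The earlier trial's claim concerned intra-operative complications, yet the timeline appears not to mark complications for recording at that point.

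*Attribution.* With crossover in both directions and analysis by allocation only, an event caused by one procedure can be reported under the other. A reader who wants to know what happens to patients who actually undergo TNLS cannot learn it from that table.

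At 27 patients per arm, one event is 1/27 = 3.7 percentage points, so a handful of minor events shapes the comparison.

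**Working it through.** The protocol states no complication, detection or crossover rate, so there is no figure of its own to reproduce. All rates below are assumptions, shown as a range. The only input from the protocol is 27 per arm (Sample size calculation).

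**Notation.** rM and rT are the true complication rates by procedure received. dT is the share of TNLS events detected, with MLS detection set to 1. cM is the share of MLS-allocated patients who receive TNLS, and cT the share of TNLS-allocated patients who receive MLS. Detection follows the procedure received, and each patient is taken to be at risk from that procedure only.

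- Observed rate, MLS arm = (1 − cM)·rM + cM·rT·dT
- Observed rate, TNLS arm = (1 − cT)·rT·dT + cT·rM
- Observed difference = (1 − cM − cT)·(rM − rT·dT)

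**Step 1. Unequal detection, equal true rates, no crossover.**

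| True rate, both | dT | MLS arm | TNLS arm | Spurious gap | Expected events of 27 |
|---|---|---|---|---|---|
| 10% | 0.75 | 10.0% | 7.5% | 2.5 points | 2.70 vs 2.03 |
| 10% | 0.50 | 10.0% | 5.0% | 5.0 points | 2.70 vs 1.35 |
| 20% | 0.75 | 20.0% | 15.0% | 5.0 points | 5.40 vs 4.05 |
| 20% | 0.50 | 20.0% | 10.0% | 10.0 points | 5.40 vs 2.70 |

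**Step 2. Crossover, equal detection (dT = 1).**

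- Equal true rates: the second bracket is 0, so the difference stays 0 whatever the crossover.
- rM = 20%, rT = 10%, 10% crossover in one direction only: 0.9 × 10 = 9.0 points instead of 10.
- The same with 10% in both directions: MLS arm 0.9 × 20 + 0.1 × 10 = 19.0%; TNLS arm 0.9 × 10 + 0.1 × 20 = 11.0%; difference 8.0 points.
- In that last case, 27 × 0.1 × 0.10 = 0.27 TNLS events are counted under MLS, and 27 × 0.1 × 0.20 = 0.54 MLS events under TNLS.

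**Step 3. Both together.** Equal true rates of 20%, dT = 0.50, 10% crossover each way: 0.8 × 10 = 8.0 points. Crossover makes the detection gap smaller, not larger.

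**The case against.** The case on the other side is strong in four places.

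1. *The MLS check is an operative step.* The sites listed are those at risk from a suspended rigid laryngoscope, which TNLS does not use. The absence of a tooth or jaw-joint check after TNLS is not unequal detection of the same event, and more such injuries after MLS would be a real difference between the procedures. This stands. What remains is that no search is named for injuries along the TNLS route.

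2. *TNLS patients are examined.* Both arms share the complications row, post-operative laryngoscopy or videostroboscopy, the same follow-up visits, and discomfort scores that include the nose. A specialist outside the study monitors safety, and serious adverse events are reported within 24 hours. This also stands, and it rules out saying that TNLS events would be noticed only by chance. It covers laryngeal findings and serious events better than minor events elsewhere along the scope's path, and it does not define what is recorded at the end of the procedure.

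3. *Intention-to-treat is valid.* It compares treatment strategies and is stated consistently. This stands; the comparison should be kept.

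4. *A by-procedure table belongs in the statistical analysis plan.* One may exist there; that plan was not available for this review. The point does not reach ascertainment, since no later analysis can recover events that were never recorded.

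A reader might infer that the comparison is tilted against MLS, and that crossover adds to the tilt by loading TNLS events onto the MLS arm. The documents support neither. No detection rate is given, so a tilt is possible but not shown. Crossover runs both ways, and Step 2 shows that with equal detection it shrinks a true difference.

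**Conclusion.** The point holds in a limited form. In an unblinded trial with complications as a comparative outcome, end-of-procedure ascertainment is described for one arm only. Unequal detection of minor events is a plausible risk, partly offset by the examinations common to both arms. Under the assumptions shown it would be worth 2.5 to 10 percentage points, or about 0.7 to 2.7 events in 27 patients. The true size is unknown because every rate is assumed.

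Analysis by allocation is not an error, but taken alone it blurs the complication profile of each procedure as performed. At an assumed 10% crossover each way, a true difference keeps 80% of its size. That pull toward zero operates whichever procedure is safer, so it would also soften a real excess of complications with TNLS. The simple model ignores that crossover patients may differ in risk, and that a patient who abandons one procedure may have events from both.

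The primary outcome is not affected.

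**What to change.** - Keep the intention-to-treat comparison of complications.
- Record for each event the procedure actually received (and, if both were attempted, which one the event followed), and add a complications table by procedure received.
- Record complications in both arms on one common form at the same time points: intra-operative or end of procedure, discharge, and 2 weeks. List the events expected of either technique and grade all entries by Clavien-Dindo. Mark the intra-operative time point in the Participant timeline.
- List separately the events found only by the MLS-specific inspection. A common form equalises the questions and their timing, not the examination itself, so this separation is needed for a fair reading.

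Cost: one form and one extra table, with no extra staff or procedure and no change to clinical management. A few more minor TNLS events may be recorded. The form needs to be in place before patients are treated.

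### The hypothesis is about the two procedures, but two-way crossover with intention-to-treat as the only stated analysis answers a policy question; a supplementary analysis would be a cheap improvement

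*Protocol*

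**What the plan says.** **Hypothesis.** The Background of the protocol closes "with hypothesis that TNLS would be non-inferior to traditional microlaryngeal surgery in benign laryngeal lesions". The wording compares one procedure with the other.

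**Margin.** Under Sample size calculation, 21 patients per group are said to be enough: "a two-arm study has a power of 80% to demonstrate a non-inferiority margin 7 absolute score", at one-sided 0.05 on VHI-30. No SD is given, and no allowance is made for crossover.

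**Crossover.** Failure of study intervention allows it both ways. A patient allocated to microlaryngeal surgery (MLS) who turns out to be contraindicated to general anaesthesia may move to TNLS. Patients allocated to TNLS who "cannot tolerate transnasal laser surgery due to discomfort or anxiety, can crossover to other study arm". No expected rate is given for either direction.

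**Analysis.** The same section ends: "Outcomes would be analyzed by intention-to-treat principle". Statistical method says: "All outcome measurements will be analyzed with an intention-to-treat principle". Neither place names a supplementary analysis or says whether the claim concerns the procedures or the policy of offering them.

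**Limits on conversion.** Inclusion criteria require that patients be "able to tolerate flexible laryngoscopy would be recruited". On the day of TNLS, "Physical examination would be repeated to ensure that the patient is fit and able to tolerate transnasal laser surgery under local anesthesia". Exclusion criteria also remove patients with local-anaesthetic allergy, unfavourable anatomy, extensive lesions or an expected difficult operation.

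**The concern.** In a superiority trial, crossover usually pulls the ITT result towards no difference and so makes the claim harder to reach. In a non-inferiority trial the same pull can make it easier. When some TNLS patients in fact have MLS, and some MLS patients have TNLS, the arms become more alike whatever the merits of the procedures.

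At stake is what a favourable result may be said to show. Followed to the letter, the protocol tests by ITT and has a hypothesis that invites the conclusion that the TNLS procedure is no worse than MLS by 7 points or more. The analysis supports a different statement: that offering TNLS, with conversion for those who cannot have it, is no worse by that amount. Where dilution operates, the error rate of the procedure claim is above the stated 5%.

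**Working it through.** **Inputs from the protocol.** Margin 7 VHI-30 points; one-sided 0.05; power 80%; 21 evaluable per arm; 20% drop-out.

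**Assumed inputs.** SD, crossover numbers, and the outcomes of patients who cross over.

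**Step 1. The plan's own figure.** Drop-out: 21 / 0.8 = 26.25, so 27 per arm and 54 in all, which reproduces. The base figure of 21 cannot be reproduced without an SD. Solving backwards at a true difference of 0 (normal approximation):

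SD = 7 / [√(2/21) × (1.645 + 0.842)] = 7 / (0.3086 × 2.486) ≈ 9.12; the t-based value is 8.97.

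I use SD 9 as the value the plan implies, and SD 16 as an assumed larger value. The latter is not taken from the minimal important difference of 16 that the protocol cites.

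**Step 2. Dilution.** Let TNLS be truly worse by D, and let crossovers respond like the arm they move to. With crossover proportions c_T and c_M:

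ITT difference = D × (1 − c), where c = c_T + c_M.

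At D = 7: one conversion in one arm (c = 1/21 = 4.8%) gives 6.67; two in one arm (c = 2/21 = 9.5%) gives 6.33; two in each arm (c = 4/21 = 19.0%) gives 5.67.

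**Step 3. Error of the procedure claim at D = 7.** This is the chance that ITT meets the margin although the procedure is worse by exactly the margin. Row one uses the noncentral t with SE = SD × √(2/21) and 40 df. Rows two and three are simulated, because the formula ignores the extra spread from mixing procedures within an arm.

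| Crossover | SD 9 | SD 16 |
|---|---|---|
| None | 5.0% | 5.0% |
| One, one arm | 6.3% | 5.7% |
| Two, one arm | 7.7% | 6.5% |
| Two in each arm | about 11% | about 8% |

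The formula at c = 20% gives 12.5% / 8.6%, which overstates the case of two in each arm.

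**Step 4. When the condition fails.** Two TNLS patients convert, and conversion itself costs them VHI-30 points (simulated):

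| Cost of conversion | ITT error, SD 9 | ITT error, SD 16 |
|---|---|---|
| 7 points | 5.0% | 4.9% |
| 14 points | 2.9% | 3.7% |

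The bias disappears, then reverses.

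**Step 5. How a comparison of patients treated as allocated behaves (SD 9, simulated).** With two crossovers each way unrelated to prognosis, its error at D = 7 is about 5%. If instead two TNLS patients convert and patients of that kind have a prognosis 14 points worse, its error is about 10.0% against 6.4% for ITT. In that case ITT meets the margin while the supplementary analysis does not in only about 0.3% of trials. So disagreement is informative, but agreement proves little.

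**The case against.** The strongest reply is that nothing here is misstated. ITT is a proper primary analysis, and the two sections agree on it. The hypothesis uses the ordinary wording of surgical trials, and its sentence goes on to anaesthetic risk, hospital expense and wider use, which sounds like a service policy. Supplementary populations are usual SAP content, and an SAP may exist that supplies one. Conversions to MLS should be few after the laryngoscopy criterion, the exclusions, the re-examination on the day and the provision for further local anaesthetic. Patients who do convert are selected, so the added analysis has its own bias.

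Most of this stands, and it sets the size of the point. It does not remove it. The protocol fixes one analysis for all outcomes beside a hypothesis about procedures, and never says that its claim is about a policy. The tolerance checks limit mainly TNLS-to-MLS conversions. Unfitness for general anaesthesia is not an exclusion and is the protocol's own example of crossover in the other direction, although ASA status is recorded pre-operatively.

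Three stronger readings are tempting, and the documents support none of them:

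- A reader might infer that ITT is the wrong primary analysis. It is valid for the policy question, and Step 5 shows that the alternative can be worse.
- A reader might infer that the trial is biased towards TNLS. With no true difference there is nothing to dilute, and harm from conversion can cancel or reverse the effect.
- A reader might infer that the true error is 11% or more. No passage gives a crossover rate, and one or two conversions in one arm raise it only modestly.

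**Conclusion.** This is a cheap improvement, not an error in using ITT. The protocol should say which question its non-inferiority claim answers, because the stated analysis answers the policy question while the hypothesis is worded about the procedures.

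The error figures in Step 3 hold only for a true deficit equal to the margin, 21 evaluable patients per arm, an SD of 9 or 16, and crossovers who respond like the arm they move to. The SD, the crossover numbers and that response are assumptions. Confidence is high on what the text says, and medium on whether the effect will matter in this trial.

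**What to change.** Keep ITT as the primary analysis, and add to Statistical method, in words such as these:

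> The primary ITT claim concerns the policy of offering TNLS, with conversion allowed when the allocated procedure cannot be carried out. Crossovers will be reported by arm and reason. As a supplementary analysis, VHI-30 will be compared in patients who received their allocated procedure, against the same margin of 7, and shown beside ITT. If the two disagree, a claim about the procedures themselves will be described as not robust. Agreement will not be taken as proof, because patients who cross over are selected.

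The supplementary analysis is not a co-primary test and does not change the ITT conclusion. The crossover rules are untouched.

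**Cost.** One more analysis of data already collected. ITT power is unchanged. The supplementary analysis has less power: 76% at 19 per arm against 80% at 21 (SD 9), or 37% against 40% (SD 16). If the procedures are truly equal and two patients cross over each way, about 6% of trials would meet the margin by ITT but not in the supplementary analysis, and so would be labelled not robust on the procedure claim. Its selection bias (Step 5) is why it should accompany ITT and not replace it.
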